While infrequently occurring (48 per 100,000), HIV infection is increased among low-income, African-American women living in the South, especially among substance users and those with STDs.^{169;170} There is increased efficiency of transmission of HIV in the presence of co-infection with bacterial STDs or trichomoniasis.¹⁷¹⁻¹⁷³ Among sexually active 14–18-year-old females in Birmingham AL, 28.7% had at least one STD (either *N gonorrhoeae*, *C. trachomatis*, or *T vaginalis*) and 5.5% had two or more and infrequent parental monitoring predicted a 2-fold increase in infection.¹⁷⁴ In 2003, 55% of African-American 11th graders in Memphis City Schools had had sexual intercourse within 3 months of the interview; 73% had ever had intercourse, while 31% reported four or more sexual partners by the 11th grade.¹⁰³

Given the health problems to be examined in the next phase of follow-up in this trial, it is important to emphasize that the NFP program reduced many of the prenatal, infant, and childhood factors discussed above that increase risk for violent antisocial behavior, psychopathology, SUDs and HIV infection.

PRELIMINARY STUDIES

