Original Sample Characteristics. We invited 1,290 women from the obstetrical clinic of the Regional Medical Center in Memphis to participate. We recruited women <29 weeks pregnant if they had no previous live births, no specific chronic illnesses thought to contribute to fetal growth retardation or preterm delivery, and at least 2 sociodemographic risks: a) unmarried, b) less than 12 years of education, c) unemployed. Eighty-eight percent (1138/1290) completed informed consent and were randomized to 1 of 4 treatment conditions described below. All low-income women in Memphis registered for prenatal care at this clinic, which meant that we enrolled nearly the entire population during the 1990–1991 enrollment period. The study was designed to follow 742 families in two treatment conditions after delivery. 92% of the women were African-American, 98% were unmarried, 67% were <19 years of age at registration, 85% came from households with incomes < federal poverty guidelines, and 9% smoked cigarettes. At randomization, there were no treatment differences in women's background characteristics.

Randomization. After the completion of informed consent and baseline interviews, identifying information on participants was entered into a computer program that randomized women to treatment conditions. The randomization methods were extensions of Soares and Wu.¹⁸² The model on which we based the randomization included 5 classification factors: maternal race, chronological age (4 levels), gestational age at enrollment, employment status of head of household and geographic region of residence (4 regions).

Statistical Power in the Original Design. We conducted power calculations to determine the number and proportion of subjects to assign to treatment and control conditions while minimizing costs in the initial study period (prenatal through child age 2). This allowed disproportionate assignment of women to treatment and control conditions and a reduction in number of families followed into the postnatal phase of the trial. Given high rates of sample retention, the original power calculations hold.

Treatment Conditions

Treatment 1 - Transportation during Pregnancy. The 166 families in this treatment condition received free round-trip taxicab transportation for scheduled prenatal care appointments. This group did not receive any postpartum services or assessments.

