Sexual Behaviors. We assessed reports of specific sexual behaviors for adolescents in the ACASI section of the interview. We assessed age of first sexual experience (oral, vaginal, and anal sex), number of lifetime male and female partners, and the number of partners in the last three months. Retrospective recall of sexual behaviors is stable for intervals as long as 3 months.^{211;212} Given that many adolescents engage in sexual behavior on infrequent or episodic bases,²¹³ we chose an assessment interval of 3 months to maximize our ability to detect sexual behavior without compromising reliability. Information will be elicited over the past 3 months on: number of different sexual partners, detailed questions on the incidence of protected and unprotected oral, vaginal, and anal sex. Additional questions addressed the number of treated sexually transmitted infections (STI) over the lifetime, whether the respondent ever had sex for money, drugs, or food. Participants estimated the number of occasions in which they engaged in protected and unprotected vaginal and anal intercourse using a format developed by St. Lawrence.²¹⁴

Risk for HIV Infection. We created an HIV risk score taking into account the following factors: gender, type of intercourse (vaginal, anal), number of partners, and the probability of sexual transmission of HIV within the Memphis/Shelby County community. The HIV risk transmission index score was created using a modified Bernoulli process model (Pinkerton and Abramson, 1998).²¹⁵ The probability of HIV acquisition was calculated as follows:

Probability of HIV acquisition =

$$\pi [1-(1-\alpha \text{UVI})^n (1-\alpha \text{PVI})^n (1-\alpha \text{UAI})^n (1-\alpha \text{PAI})^n]$$

- “ π ” represents the prevalence of HIV within a population. Prevalence of HIV in Shelby County in 2012 was estimated at a rate of 655.6 for African American and 139.3 for Caucasian per 100,000 (Shelby County Health Department, 2012). Mother's race at intake was used for child's race.
- “ n ” represents the number of acts performed over a three month period
- “ α ” represents the probability of HIV transmission per sexual act. Sexual acts are

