The primary analyses made use of general linear model methods and their extensions. The focus was on full model specification to account for all sources of variation, and a full examination of interactions among model factors. The primary classification factors for examination in our models, as determined by our hypotheses and earlier work, include treatments (Control vs. Nurse Visited - T), maternal psychological resources (low versus high – P), and sex of child (S). Standard covariates included an index of household poverty, maternal beliefs associated with child abuse, and for child outcomes, age of the child at the 18-year interview. Genetic analyses included the gene as an additional classification factor and were interacted with treatment status only (see more information below). We employed pared-down versions of full model specification when we had infrequently occurring outcomes (e.g. convictions for interpersonal violence). In general the approach involved beginning with a fully specified model and continuing to eliminate non-significant interactions unless a specific a priori hypothesis forced the interaction term(s) into the model.

Continuous variables were run with a general linear model; dichotomous variables with binomial error distributions; low frequency count variables with negative binomial distributions. For outcomes measured over the life course, the above models were extended to mixed or generalized mixed models to account for correlated data (random effects for time with unstructured variance terms). Subsequent children analyses were also run with mixed or generalized mixed models to account for correlation within the same family. We were interested in the treatment effects for subsequent children alone, as opposed to an overall family effect that would include the first born children.

We employed Cox proportional hazard models²³² for outcomes with a survival component. We present in the tables adjusted hazard rates at age 18 since the vast majority of the sample was interviewed after their 18th birthday but rapidly drops off after this date. The methods used for the mortality analyses can be found elsewhere.¹¹

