Inclusion of Gene Activity Classification Factors. Some of our models included classification factors for functional classifications (activity variants) of the polymorphisms hypothesized to moderate program impact in this trial (5-HTTLPR, MAOA-LPR, and COMT Val158Met); we were not interested in genotypes per se, but rather functional classes that group genotypes by activity level (low – L, high - H or intermediate - I). In the case of 5-HTTLPR, L_G and S alleles are both low-activity variants that lead to low expression; from the analysis standpoint, the low-activity genotypes (L_G/L_G, S/S, and L_G/S) were grouped into the low-activity class; the high activity genotypes (L_A/L_A) into a high-activity class; and the remaining genotypes (L_A/L_G and L_A/S) grouped into an intermediate class. We used a similar approach with MAOA-LPR and COMT Val158Met. In the case of the X-linked MAOA-LPR, we grouped males into high and low expression allele groups and excluded females from analyses. In the COMT Val158Met analyses, we excluded non-African ancestry participants.

Tests of Hypotheses

Maternal Outcome Hypotheses

Hypothesis 1 (primary): The program will continue to improve maternal life-course reflected in total costs for welfare (SNAP, AFDC/TANF, and Medicaid), especially for mothers with high psychological resources. We tested Hypothesis 1 by examining the primary maternal life-course outcome (public expenditures for SNAP, AFDC/TANF and Medicaid) in our primary model, estimating public expenditures for these benefits over time, which included a factor for T and P, the interaction between these classification factors (T x P), and a set of covariates. For the public benefit expenditure outcome, we analyzed the data in mixed models that included, in addition to the core model terms, women as levels of a random factor, a fixed repeated measures classification factor for time (first-born child age) of assessment, and all interactions of time with the other fixed classification factors. We examined the treatment–control difference summing across levels of maternal psychological resources, and conducted planned contrasts for women in the high-resource group.

Hypothesis 2 (secondary). The program will reduce maternal SUDs and depression. We examined SUDs and depression by examining planned contrasts within the classification structure specified for Hypothesis 1, using generalized linear models, logistic for depression and SUD.

Child Outcome Hypotheses

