Hypothesis 3a–d (primary): The program will improve the health and development of firstborn children who will exhibit: a) superior cognitive, language, and academic functioning; b) less depression and anxiety; c) less gang membership, and fewer arrests, convictions, and self-reported antisocial behavior - especially for crimes involving interpersonal violence.. We will examine this hypothesis in the model used to test hypotheses 1 and 2, after adding child sex (S) as a classification factor. We will test hypotheses 3a–d by examining each of child outcome in the saturated TxPxS (2x2x2) model, including covariates. In our first-level analysis, we will examine treatment–control differences averaging across levels of maternal psychological resources and child sex. Outcomes that have essentially normal distributions (e.g., cognitive and academic outcomes) will be examined in the general linear model. Those that have low-frequency count distributions (e.g., counts of failed conduct grades) will be examined in the generalized model. For very sparsely distributed outcomes, we may need to drop certain model terms, such as 3-way interactions or nonsignificant covariates to increase model stability. We will retain model terms with highest levels of significance and those central to the hypothesis. Finally, we will examine outcomes that have binomial distributions in the fully specified logistic model. Some outcomes, such as standardized math scores, will have multiple measures for each child at different ages, and the model will include additional repeated measures factors for child age.

Hypothesis 4 a–c (primary): The program will reduce youth risk for a) HIV infection, b) pregnancies, births, c) use of substances, and SUDs. We will employ nearly identical analytic methods for testing hypothesis 4 as we employ for testing hypothesis 3. The primary outcome(s) for HIV risk will consist of indices that we will create to quantify HIV risk exposure.

Hypothesis 5 (secondary): The program will improve firstborn children’s executive cognitive functioning (ECF); and rates of high school graduation. We will employ nearly identical analytic methods

for testing hypothesis 5 as we employ for testing hypothesis 3.. In analysis of executive cognitive functions, we will control statistically for KBIT matrices scores and PPVT to discern the impact of the program on executive functions independent of general intelligence and language.

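### The stated models leave out all five randomisation factors; adding them is a cheap, small gain in precision, and no stated result is invalid without it

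*Protocol*

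**What the plan says.** Under Randomization, the protocol states: "The model on which we based the randomization included 5 classification factors: maternal race, chronological age (4 levels), gestational age at enrollment". The same sentence adds employment status of the head of household and region of residence (four regions).

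Under Statistical Models and Methods of Analysis, the classification factors are treatment (T), maternal psychological resources (P) and child sex (S). The covariates follow: "Standard covariates included an index of household poverty, maternal beliefs associated with child abuse, and for child outcomes, age of the child".

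The Tests of Hypotheses section adds little. Hypothesis 1 uses a model "which included a factor for T and P, the interaction between these classification factors (T x P), and a set of covariates", with time as a repeated factor. Hypothesis 3 tests each child outcome "in the saturated TxPxS (2x2x2) model, including covariates". Later hypotheses add gene activity class and, for executive function, the KBIT matrices and PPVT scores.

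Race or ancestry enters in only two ways. It restricts a genetic analysis ("In the COMT Val158Met analyses, we excluded non-African ancestry participants"), and it is an input to the HIV-risk index, where mother's race stands in for the child's: "Prevalence of HIV in Shelby County in 2012 was estimated at a rate of 655.6 for African American and 139.3 for Caucasian per 100,000".

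**The concern.** Balanced allocation removes chance differences in the balancing factors. If the model then ignores those factors, their variance stays in the residual and the reported standard error is wider than the true sampling variation. The section also says it aims at full model specification, and leaving out the factors that shaped allocation sits oddly with that. Poverty and child-abuse beliefs were kept because the arms differed on them at baseline (Research Activities for Current Phase of Follow Up). No reason is given for leaving out the randomisation factors.

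What is at stake is a little power for 18-year outcomes in a sample whose size is fixed. Race is the clearest case: it was a randomisation factor, it directly sets part of a primary outcome, and it was associated with not being seen at 18 years. The protocol reports no attrition bias by treatment, so no bias is claimed here.

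There is a related conflict in the text. Original Sample Characteristics says the treatment groups did not differ on background characteristics at randomisation. Research Activities for Current Phase of Follow Up says control and nurse-visited women did differ at randomisation on poverty and beliefs.

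**Working it through.** **Inputs.** Youth assessed at 18 years: 435 control + 194 nurse-visited = 629 (Table 2). The factors cost about 9 df if race and employment are binary (1 + 1), gestational age is linear (1), and age and region have four levels each (3 + 3). The two-sided 0.05 level and every R² (extra outcome variance explained) are assumptions; the protocol gives none.

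**Linear outcomes, balance kept.** Let k = √(1 − R²). Standard errors without the factors are too wide by 1/k − 1. Where the adjusted test has 80% power, the unadjusted test has 1 − Φ(1.96/k − 2.8016). Its true size is 2[1 − Φ(1.96/k)].

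| R² | SE too wide | Power | Size |
|---|---|---|---|
| 2% | 1.0% | 79.4% | 0.048 |
| 5% | 2.6% | 78.5% | 0.044 |
| 10% | 5.4% | 76.9% | 0.039 |

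Size never exceeds 0.05. A simulation with covariate-balancing 514:228 assignment and race-dependent dropout agreed. Bias was at most 0.004 SD with or without the factors. At R² 10%, type I error was 4.2% unadjusted and 5.1% adjusted, and power at an effect size of 0.20 was 64.1% and 67.7%.

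**Linear outcomes, balance lost.** The SE ratio, omitted to included, is √[(1 − 9/628)/(1 − R²)] = 1.003, 1.019 and 1.047 at R² 2%, 5% and 10%. Unadjusted power is then 79.8%, 78.5% and 76.3% against 80%. At R² 1% the ratio is √(0.9857/0.99) = 0.998, so adjustment costs slightly more than it gains. Break-even R² is about df/617 (617 being roughly the residual df): 1.46% for all factors, 0.65% for race plus age (4 df) and 0.16% for race alone.

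**Non-linear outcomes.** Simulated at 435/194 with one balanced prognostic score and no df cost.

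| Model | R² | Effect, omitted v included | Power, omitted v included |
|---|---|---|---|
| Logistic (10,000 runs) | 2% | OR 0.609 v 0.603 | 72.7% v 73.7% |
| | 10% | OR 0.627 v 0.601 | 69.2% v 73.1% |
| Cox (1,500 runs) | 2% | HR 0.649 v 0.646 | 67.4% v 68.1% |
| | 10% | HR 0.663 v 0.652 | 65.2% v 68.1% |
| Negative binomial (1,500 runs) | 2% | IR 0.597 v 0.595 | 79.2% v 80.3% |
| | 10% | IR 0.599 v 0.593 | 73.9% v 79.1% |

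Assumed settings: logistic, baseline risk 35% and log OR −0.5; Cox, HR 0.65 and control cumulative hazard 0.35; negative binomial, control mean 0.5, dispersion 1.5 and IR 0.60. The odds and hazard ratios move slightly towards 1 when the factors are omitted, because the estimand becomes more marginal. The negative binomial rate ratio, used for "low frequency count variables with negative binomial distributions", is not attenuated.

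**HIV-risk index.** The index is prevalence times a behavioural term. Race's share of its variance is Var(prev)/[Var(prev) + E(prev²)·CV²]. Here Var(prev) = q(1 − q)·516.3², with 655.6 − 139.3 = 516.3, and CV² = (1 + c²)/0.55 − 1. The 0.55 is the protocol's survey figure ("55% of African-American 11th graders in Memphis City Schools had had sexual intercourse within 3 months of the interview"). The CV among active youth, c, is assumed to be 1 to 2, giving CV² of 2.64 to 8.09.

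- q = 34/629 = 0.054, using the 34 youth of mainly European ancestry as a proxy and assuming all 629 were genotyped. With c = 1: 13,630/(13,630 + 407,627 × 2.636) = 1.25%. With c = 2: 0.41%.
- q = 0.08, coding every mother who was not African-American at the Caucasian rate: 1.84% and 0.61%.

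So race explains about 0.4-1.8% of variance, or 0.2-0.9% in SE, taking behaviour as equal by race. That is small, but above the 0.16% break-even for one df.

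**Baseline statements.** Preliminary Studies gives 98% unmarried, 67% under 19 and 92% African-American for all 1,138 randomised women. Original Sample Characteristics repeats those percentages. Its claim of no differences may therefore cover four arms, while the later statement compares only control with nurse-visited. Neither section says so.

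**The case against.** The strongest reply is that nothing here is an error. The analysis is unbiased and, for linear outcomes, conservative. The protocol says standard covariates *included* three items, which may not be a closed list, and a final list may sit in an analysis plan that is not shown. The gain rests on an unknown R² that may well be low. The protocol found little variation among neighbourhoods, the sample is 92% African-American and 67% under 19, and the poverty index and psychological resources already in the model may overlap with employment. The non-linear simulations charge nothing for 9 df. The Cox and negative binomial power figures have a Monte Carlo error of about 1 point, as large as the differences at R² 2%. At a 3% event rate, 10-17% of simulated logistic fits with the extra terms failed or separated. Adding models after the fact also adds flexibility.

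Most of this stands as a limit on size, and it is why the point is minor. It does not remove the point. The protocol names its covariates and model terms in detail and leaves out exactly the factors that shaped allocation. The instability with rare outcomes calls for a shorter covariate set, and side-by-side labelling deals with the flexibility. The conflict over baseline balance is a separate matter of wording and does not depend on R².

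**Conclusion.** The concern holds as a minor one. None of the five randomisation factors is in any stated model. Type I error is not inflated and no bias is claimed. For linear outcomes the loss is about 0.6 to 3.1 power points from 80% if balance holds and the factors add 2-10% of variance. If balance is lost it is 0.2 to 3.7 points, and there is no net gain from adjusting below an R² of about 1.5%. An R² of 20-30% would give more: at an effect size of 0.20, power of 63.9% would rise to 73.6-79.1%. Nothing in the protocol supports an R² that high. For logistic and Cox outcomes, the shift in the effect is a different estimand and not an error. The 18-year result tables are not in the text available, so the statement that no result is invalid rests on method and not on re-analysis.

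**What to change.** - Add the five randomisation factors as fixed covariates, about 9 df under the coding above. Keep poverty and beliefs as they are.
- For sparse outcomes use a reduced set, race and maternal age, in line with the protocol's own paring-down of models. Include race at least for the HIV-risk index.
- The methods section describes some analyses as already done. For those, report the factor-adjusted model beside the model as specified and label it as added later.
- State which sample each baseline claim describes: all 1,138 randomised women, or the 742 in treatments 2 and 4.

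No data collection is needed: the factors were used to randomise, and the protocol reports complete background data. The costs are a few more parameters, a second set of estimates, and conditional odds and hazard ratios that are not interchangeable with the unadjusted ones.
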